## **Template Instructions**

### **Sections that do not apply:**

- *In several sections, the addition of checkboxes for **Not Applicable** have been added to the template as responses.*
  - *If an N/A checkbox is present, select the appropriate justification from the list.*
  - *If an N/A checkbox is not present, or if none of the existing checkboxes apply to your study, you must write in your own justification.*
- *In addition:*
  - *For research where the only study procedures are records/chart review: Sections 19, 20, 22, 23, 24, 25, 31, and 32 do not apply.*
  - *For exempt research: Sections 31 and 32 do not apply.*

### **Studies with multiple participant groups:**

- *If this study involves multiple participant groups (e.g. parents and children), provide information in applicable sections for each participant group. Clearly label responses when they differ. For example:*

Response:

Intervention Group:

Control Group:

### **Formatting:**

- *Do not remove template instructions or section headings when they do not apply to your study.*

*If you are pasting information from other documents using the “Merge Formatting” Paste option will maintain the formatting of the response boxes.*

### **Amendments:**

- *When making modifications or revisions to this and other documents, use the **Track Changes** function in Microsoft Word.*
- *Update the version date or number **on Page 3.***

**GRANT APPLICABILITY:**

*Indicate whether this protocol is funded by a grant (e.g. NIH, foundation grant).  
For a grant with multiple aims, indicate which aims are covered by this research  
proposal.*

*NOTE: This question does not apply to studies funded by a sponsor contract.*

 *Include a copy of the grant proposal with your submission.*

Response: Astra Zeneca

### 1.0 Objectives

*1.1 Describe the purpose, specific aims, or objectives of this research.*

Response:

**Hypothesis 1:** Addition of dapagliflozin results in increased levels of ketone bodies in basal and insulinopenic conditions in Type 1 diabetes (T1D) compared to addition of exenatide/Exenatide extended release.

**Aim 1.1:** To compare levels of ketone bodies (beta-hydroxybutyrate and acetoacetate) in plasma and urine in basal state and in insulinopenic state following single doses treatments before and after 12 weeks treatment with dapagliflozin, exenatide/Exenatide extended release, a combination of both drugs or placebo in T1D.

**Aim 1.2:** To evaluate levels of FFA, glycerol, diglycerides and hormone sensitive lipase (HSL) in plasma in basal state and in insulinopenic state following single doses treatments before and after 12 weeks treatment with dapagliflozin, exenatide/Exenatide extended release, a combination of both drugs or placebo in T1D.

**Aim 1.3:** To measure and compare electrolytes, serum bicarbonate, cortisol and catecholamines in basal state and in insulinopenic state following single doses treatments before and after 12 weeks treatment with dapagliflozin, exenatide/Exenatide extended release, a combination of both drugs or placebo in T1D.

**Hypothesis 2:** Addition of dapagliflozin induces hyperglucagonemia in basal and insulinopenic conditions in T1D compared to addition of exenatide/Exenatide extended release.

**Aim 2.1:** To compare glucagon, glucose and GLP-1 levels in basal state and in insulinopenic state following single doses treatments before and after 12 weeks treatment with dapagliflozin, exenatide/Exenatide extended release, combination of both drugs or placebo in T1D.

**Aim 2.1:** To correlate changes in glucagon and FFA concentrations, ketone bodies levels with total daily insulin dose following 12 weeks of treatment.

**Hypothesis 3 (exploratory):** Dapagliflozin treatment induces lipolysis in adipose tissue in basal and insulinopenic conditions in T1D compared to addition of exenatide/Exenatide extended release.

**Aim 2.1:** To evaluate FFA, glycerol and HSL levels in adipose tissue extracts in basal state and in insulinopenic state following single doses treatments before and after 12 weeks treatment with dapagliflozin, exenatide/Exenatide extended release, combination of both drugs or placebo in T1D.

**Aim 2.2:** To investigate the expression of SGLT-2 in adipose tissue and correlate it with FFA and ketone body generation in basal state and in insulinopenic state following single doses (acute) treatments before and after 12 weeks (long term) treatment with dapagliflozin, exenatide (acutely)/Exenatide extended release (long term), a combination of both drugs or placebo in T1D.

1.2 *State the hypotheses to be tested, if applicable.*

*NOTE: A hypothesis is a specific, testable prediction about what you expect to happen in your study that corresponds with your above listed objectives.*

Response:

**Hypothesis 1:** Addition of dapagliflozin results in increased levels of ketone bodies in basal and insulinopenic conditions in Type 1 diabetes (T1D) compared to addition of exenatide/Exenatide extended release.

**Hypothesis 2:** Addition of dapagliflozin induces hyperglucagonemia in basal and insulinopenic conditions in T1D compared to addition of exenatide/Exenatide extended release.

**Hypothesis 3 (exploratory):** Dapagliflozin treatment induces lipolysis in adipose tissue in basal and insulinopenic conditions in T1D compared to addition of exenatide/Exenatide extended release.

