## 17.0 Data Management and Analysis

17.1 *Describe the data analysis plan, including any statistical procedures. This section applies to both quantitative and qualitative analysis.*

Response: **DATA ANALYSIS**

This is a prospective study to evaluate ketogenic stress before and after 12 week treatment with dapagliflozin and exenatide/Bydureon. The similarities in baseline values between the study groups will be compared using appropriate parametric tests. Transformations of the data on order to meet statistical assumptions may be considered. All statistical analysis will be carried out using SPSS software (SPSS Inc, Chicago, Illinois) based on intention to treat principle. Data will be presented as mean± standard error. *Data will not be imputed to replace missing data and only observed data will used to run the mixed model for repeated measurement (MMRM) analysis. The primary endpoint of the study is to detect a significant difference in the percent change in beta-hydroxybutyrate and acetoacetic acid (total ketone bodies) in the plasma samples following 12 weeks of dapagliflozin treatment compared to placebo. *Fasting samples collected at weeks 0, 1, 4, 8 and 12 will be used for this comparison with values at week 0 considered as baseline. The statistical analysis will be done using MMRM with assigned  $\alpha$  value of 0.05. There is no previous data on effects of dapagliflozin alone on ketone bodies generation in T1D but our preliminary data on 12 weeks treatment with**

dapagliflozin in patients with T1D using insulin and liraglutide shows more than a 2 fold increase in total ketone bodies.

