The secondary end points include the *comparison of the acute changes in AUC0hr-6hr of ketone bodies (plasma and urine), FFA and glucagon between dapagliflozin, exenatide, combination of both and placebo before and after 12 weeks of treatment period using Paired t-test for within group comparisons and student t-test for between groups comparisons.* Additional secondary end points include comparison of basal plasma glucagon, FFA and urinary ketone bodies changes after 12 weeks of dapagliflozin and Bydureon or combination of both treatments compared to baseline using paired t-test and to placebo using 2-way RMANOVA. Changes in insulin dose, glucose levels and carbohydrate intake will be compared after 12 weeks of dapagliflozin and Bydureon treatments to baseline using paired t-test and to placebo with 2-way RMANOVA. Changes in lipolysis mediator (HSL) in plasma and expression of HSL and SGLT-2 in adipose tissue and MNC will be compared to baseline using paired t-test and to placebo with t-test.

*17.2 If applicable, provide a power analysis.*

*NOTE: This may not apply to certain types of studies, including chart/records reviews, survey studies, or observational studies. This question is asked to elicit whether the investigator has an adequate sample size to achieve the study objectives and justify a conclusion.*

*Response:* Conservatively estimating a difference in the change from baseline in ketone bodies generation between the dapagliflozin and placebo of 50%, with standard deviation of no more than 50%, a sample size of 20 patients per group (assuming a drop-out rate of 15%) should provide adequate power ( $\beta = 0.2$ ) to detect a significant difference ( $\alpha = 0.05$ ). A total of 80 patients will be recruited for the study.

*17.3 Describe any procedures that will be used for quality control of collected data.*

*Response:* Data will not be imputed to replace missing data and only observed data will be used to run the mixed model for repeated measurement (MMRM) analysis

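### Hypotheses 1 and 2 compare dapagliflozin with exenatide ER in the basal state, but section 17.1 names no such contrast

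*Combined protocol and SAP*

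**What the plan says.** Section 1.2 lists the hypotheses to be tested. Hypothesis 1 predicts that adding dapagliflozin raises levels of "ketone bodies in basal and insulinopenic conditions in Type 1 diabetes (T1D) compared to addition of exenatide/Exenatide extended release". Hypothesis 2 does the same for glucagon: "Addition of dapagliflozin induces hyperglucagonemia in basal and insulinopenic conditions in T1D compared to addition of exenatide/Exenatide extended release". Only Hypothesis 3 is labelled exploratory.

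The aims in section 1.1 repeat the basal comparison across the four treatments. Aim 1.1 is "To compare levels of ketone bodies (beta-hydroxybutyrate and acetoacetate) in plasma and urine in basal state and in insulinopenic state". The first of the aims numbered 2.1 is "To compare glucagon, glucose and GLP-1 levels in basal state and in insulinopenic state".

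Section 17.1 then sets out three relevant analyses:

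- **Primary, basal plasma ketones.** An MMRM on fasting samples from weeks 0, 1, 4, 8 and 12 assesses percent change "following 12 weeks of dapagliflozin treatment compared to placebo".
- **Secondary, basal glucagon, FFA and urinary ketones.** The plan gives a "comparison of basal plasma glucagon, FFA and urinary ketone bodies changes after 12 weeks of dapagliflozin and Bydureon or combination of both treatments", and these are "compared to baseline using paired t-test and to placebo using 2-way RMANOVA".
- **Secondary, acute test.** The 0 to 6 hour AUC is compared for plasma and urine ketones, "FFA and glucagon between dapagliflozin, exenatide, combination of both and placebo before and after 12 weeks of treatment period", with Student's t-test between groups.

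Under section 10.1 (Visits 2 and 6), the acute procedures after the baseline samples apply to pump patients only. Section 6.1 also admits patients on multiple daily injections.

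**The concern.** The basal tests use a different comparator from the basal hypotheses. The hypotheses ask whether ketones and glucagon are higher on dapagliflozin than on exenatide ER. The tests ask whether they differ from placebo or from baseline. An analyst who follows section 17.1 exactly will test the insulinopenic limb of each hypothesis against the stated comparator, but not the basal limb.

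The acute AUC analysis cannot stand in for it. It measures the response to stopping insulin, and it leaves out patients on multiple daily injections, whose ketone and glucagon data are all basal.

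At stake is whether half of each of two stated hypotheses gets a direct estimate with its own uncertainty, or is argued from two separate comparisons with placebo.

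**Working it through.** **Step 1. Set hypotheses against tests.**

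| Outcome and state | Comparator in section 1.2 | Comparator in section 17.1 | Dapagliflozin v exenatide named? |
|---|---|---|---|
| Plasma ketones, basal | exenatide ER | placebo (dapagliflozin arm only) | No; no exenatide ER test at all |
| Urinary ketones, basal | exenatide ER | baseline, placebo (each active arm) | No |
| Glucagon, basal | exenatide ER | baseline, placebo (each active arm) | No |
| Ketones and glucagon, insulinopenic | exenatide | all four arms, AUC 0 to 6 h | Yes, within the between-group t-tests |

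The only other between-group test in section 17.1, of similarity at baseline, concerns balance before treatment and not treatment effect.

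**Step 2. What the planned models could supply.** Write D, E and P for the mean changes on dapagliflozin, exenatide ER and placebo. In one unadjusted four-arm model, (D − P) − (E − P) = D − E. For basal glucagon and urinary ketones both placebo contrasts are planned, so the point estimate can be recovered. Its interval cannot be read off the two placebo intervals, because they share the placebo arm. With n per arm and common SD σ, each placebo contrast has variance 2σ²/n and their covariance is σ²/n. So Var(D − E) = 2σ²/n + 2σ²/n − 2σ²/n = 2σ²/n. Treating the two as independent would give 4σ²/n, an interval about 1.41 times too wide. The contrast therefore has to be requested from the model. For fasting plasma ketones E − P is not planned either, so nothing can be recovered.

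**Step 3. Reproduce the plan's sample size.** Section 17.2 uses a 50% difference, SD 50%, α 0.05 (two-sided taken), power 80% and 15% drop-out. The two-sample t-test needs 16.7, so 17 per group (power 0.807), and 17/0.85 = 20. The stated 20 per group reproduces, but it is built on dapagliflozin versus placebo.

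**Step 4. Precision of the missing contrast, plasma ketones.** Carry over SD 50 and 15% drop-out (assumptions).

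- Cohort 1 alone: 15 × 0.85 = 12.75 completers per arm, so 12 or 13.
- Both cohorts, with a near-equal split of cohort 2 (assumption): (15 + 20/3) × 0.85 = 18.4, so 18 or 19.

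Half-width of the 95% CI = t(0.975, 2n − 2) × 50 × √(2/n):

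| n per arm | 50 × √(2/n) | t | Half-width (percentage points) |
|---|---|---|---|
| 12 | 20.41 | 2.074 | 42.3 |
| 13 | 19.61 | 2.064 | 40.5 |
| 18 | 16.67 | 2.032 | 33.9 |
| 19 | 16.22 | 2.028 | 32.9 |

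**Step 5. Cost of a cohort term.** Take 13 v 13 in cohort 1 and 6 v 5 in cohort 2. The information is 13×13/26 + 6×5/11 = 6.50 + 2.73 = 9.23, so SE = 50/√9.23 = 16.46. With 37 − 3 = 34 df the half-width is 2.032 × 16.46 = 33.5. The term costs almost nothing.

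These are simple week-12 comparisons that take no credit for repeated measures. The documents give no SD for glucagon or urinary ketones, so no figure is offered there. Nor do they give an expected dapagliflozin versus exenatide ER difference, so no power is claimed.

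**The case against.** The best defence is that the comparison is already in the protocol. Sections 1.1 and 1.2 fix the outcomes, the state, the comparator and the direction. A reader might infer that any basal dapagliflozin versus exenatide ER result would be post hoc. The documents do not support that: the comparison is pre-stated, and what is missing is its test.

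A reader might also infer that the basal limb could be reached only by an indirect comparison through placebo. That too goes too far for glucagon and urinary ketones. The sentence on the 2-way RMANOVA mentions all three active regimens and placebo, a single four-arm model is a natural reading, and step 2 shows that it contains the direct difference. The defence stands to that extent. It does not reach fasting plasma ketones, where section 17.1 names one active arm and one comparator.

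A third inference is that the missing placebo arm in cohort 2 (section 4.1) makes this gap worse. It does not belong here. It follows from the cohort 2 design and would remain if this contrast were added.

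Finally, it is fair to say that the primary comparison and its sample size agree with each other, and that a wording mismatch may be the whole problem. That supports a modest rating. It does not remove the need for hypotheses and tests to match.

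**Conclusion.** The point holds in a limited form. Section 17.1 names no basal dapagliflozin versus exenatide ER contrast, although Hypotheses 1 and 2 call for one. Fasting plasma ketones have no exenatide ER test at all. For basal glucagon and urinary ketones the contrast is derivable from a four-arm model but has no stated test or interval. This should be fixed, and it does not touch the primary endpoint.

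The half-widths in step 4 show how precise the added contrast would be; they do not measure harm from its absence. They rest on the dapagliflozin versus placebo SD and drop-out carrying over. The pooled figures also need the cohorts to be combined and cohort 2 to split nearly equally, neither of which the documents state.

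**What to change.** Keep dapagliflozin versus placebo as the primary comparison. In section 17.1:

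- State that the fasting-ketone MMRM is fitted to all arms, and add as a secondary contrast the week-12 dapagliflozin minus exenatide ER difference in fasting plasma total ketones, with its 95% CI.
- Add the same contrast, with its 95% CI, to the repeated-measures analyses already planned for basal glucagon and basal urinary ketones. No replacement models are needed.
- Include a cohort term wherever the cohorts are pooled. If glucagon is pooled, say so, because section 10.1 describes cohort 2's purpose in terms of ketogenesis only.

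Alternatively, if the basal head-to-head comparison was never intended, reword the basal limb of Hypotheses 1 and 2 to name placebo as comparator, and bring the aims into line.

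The cost is wording and one contrast per outcome. No new samples are needed: section 2.1 has ketones and glucagon measured in all blood samples and ketones in all urine samples. The downside is limited precision, so each contrast is best reported mainly as an estimate with its interval.

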## 2.0 Scientific Endpoints

2.1 *Describe the scientific endpoint(s), the main result or occurrence under study.*

*NOTE: Scientific endpoints are outcomes defined before the study begins to determine whether the objectives of the study have been met and to draw conclusions from the data. Include primary and secondary endpoints. Some example endpoints are: reduction of symptoms, improvement in quality of life, or survival. Your response should **not** be a date.*

Response:

The study investigations include evaluation of the acute effects of a single dose of dapagliflozin (10mg), exenatide (5µg), a combination of exenatide and dapagliflozin or placebo under insulinopenic condition and the long term effect under basal conditions before and after 12 weeks treatment with dapagliflozin, Exenatide extended release, a combination of Exenatide extended release and dapagliflozin or placebo on ketogenesis, glucagon and lipolysis.

In the acute effects study, qualified patients will come fasting to the research center. Review of study procedures and vitals will be performed. Insulin infusion (pump) will be

stopped and basal blood, urine and adipose tissue biopsy samples will be obtained. Placebos, exenatide (5µg) or dapagliflozin (10mg) (with appropriate placebos) or combination of exenatide and dapagliflozin will be administered, according to a randomized fashion, and blood samples will be collected every 30 min for up to 8 hours after starting the treatment. Urine will be collected every hour up to 8 hours and a second adipose tissue biopsy will be collected at 6 hours after the start of the treatment. Additional blood samples will be collected at 1, 2, 4 and 6 and 8 hour marks for MNC isolation. Plasma and mononuclear cell (MNC) fractions will be prepared from the blood samples. The patient will then come back at the 24 hour mark for a fasting blood and urine collection. The long term study will then commence. Exenatide extended release or dapagliflozin (along with appropriate placebos) or a combination of both drugs will be started and continued for 12 weeks according to original randomization of day 0. In the long term study, dapagliflozin (or the appropriate placebo) will be started at 5mg dose and will be titrated to 10mg/day after 5 days. Fasting blood and 24hr urine samples will be collected at 1, 4 and 8 weeks. At 12 weeks, the 2nd acute effects testing study will be repeated as described above.

Measurements of beta-hydroxybutyrate, acetoacetic acid, glucose, FFA and glucagon, will be measured from all blood samples collected. HSL, GLP-1, glycerol, electrolytes, serum bicarbonate, cortisol and catecholamines will be measured at 0, 60, 120, 240, 360, 480 min and at 24hr following single dose studies at 0 and 12 weeks visits and at baseline on the 1, 4 and 8 weeks visits. Ketone bodies will be measured in all urine samples. All MNC and adipose tissue samples will be tested for HSL and SGLT2 expression.

### 3.0 Background

*3.1 Provide the scientific or scholarly background, rationale, and significance of the research based on the existing literature and how it will contribute to existing knowledge. Describe any gaps in current knowledge. Include relevant preliminary findings or prior research by the investigator.*

*Response:*

Insulin therapy in patients with type 1 diabetes was started soon after the discovery of insulin. Majority of such patients are still not at their glycemic targets. Clearly, therefore, it is necessary to look for means of further improvement. Novel approaches with GLP-1 receptor agonists (GLP-1RA) like liraglutide and with sodium-glucose transport protein-2 (SGLT2) inhibitors, have recently provided additional strategies for the treatment of this condition when used in combination with insulin (1-5). Initial studies with either liraglutide or dapagliflozin,(5-7) an SGLT2 inhibitor, have been successful but have still not allowed patients to be at their target level of glycemic control. We have, therefore, pioneered the use of ‘triple therapy’, combining insulin, GLP-1RAs and SGLT-2 inhibitors.

While the search for new and novel strategies for glycemic control in type 1 diabetes is of great significance, it is also important to evaluate these new therapies for their associated risks and effects on known complications of type 1 diabetes such as Diabetic Ketoacidosis (DKA). DKA is an important complication and cause of mortality and morbidity in type 1 patients. The decreased ratio of insulin to glucagon in insulin deficient subjects promotes ketogenesis (8). In patients with type 1 diabetes, the suppressive effect of hyperglycemia

and the paracrine inhibitory effect of insulin and GABA from the  $\beta$  cell on  $\alpha$  cell are absent. Thus, plasma glucagon concentrations are elevated and in combination with insulin deficiency, lead to lipolysis, increased plasma FFA concentrations and an increased fatty acid supply to the liver. Thus, both fatty acid oxidation and ketogenesis are enhanced (9).

Data from recent studies, including our own (2), show that GLP-1RA can lower blood glucose concentrations in patients with type 1 diabetes through their protean actions, independently of the beta cell. These actions include suppression of appetite and carbohydrate intake, slowing of gastric emptying and the suppression of glucagon. Our recent work has shown that liraglutide not only markedly suppresses the post prandial excursion of glucagon, it also suppresses fasting plasma FFA concentrations (Fig 1). In this context, it is important that the deletion of the glucagon receptor protects both from hyperglycemia and ketosis following a high dose of streptozotocin in mice (10). Therefore, it is possible that GLP-1 mimetics may protect from DKA in presence of sufficient insulin.

SGLT-2 inhibitors are of special importance since their mode of action is independent of insulinogenesis. They are selective antagonists to sodium-glucose transporter in the proximal convoluted tubules in the kidneys. They act by inhibiting glucose re-absorption in the renal tubules and thus inducing the excretion of 60-100 grams per day of glucose in urine (7). They have been studied extensively for use in type 2 diabetes however; there is still paucity of data regarding any benefits in type 1 diabetes. Recent studies have shown that they have similar effects of enhanced 24 hour urine glucose excretion in type 1 diabetes, just like in patients with type 2 diabetes with improved glycemic indices. Indeed, Mudaliar et al (3) demonstrated that use of remogliflozin in patients with type 1 diabetes significantly reduced glucose concentrations relative to a placebo after a standard glucose load and glucose improvements were sustained for up to 10 hours. Perkins et al (6) studied use of 8 weeks of empagliflozin in type 1 diabetes and demonstrated significant reduction in HbA1c, fasting blood glucose, the rate of hypoglycemia and the daily insulin dose. Mean urinary excretion of glucose increased and significant weight loss was observed. Cherney et al(1) also demonstrated significantly increased glucose excretion and fall in HbA1c despite lower insulin doses with use of empagliflozin 25mg daily for 8 weeks in patients with type 1 diabetes.

